Risk / Benefit Assessment	The safety of manual therapy care in infants has been the subject of review (Carnes et al 2016, Dobson et al 2008). The reported incidence and prevalence of moderate and serious adverse events is very low with this form of gentle light touch therapy. Manipulation using manual thrust techniques are contra-indicated in this patient population and none will be used in this study. We expect this to be a very low risk of harm study in both arms of the trial especially as the treatment is very gentle and the condition is usually self-limiting and resolving.

Objective(s)	This study will explore whether targeted specific osteopathic light touch is superior to non-specific light touch in reducing average daily crying time over two weeks in unsettled crying infants. Secondary objectives are to measure effects on confidence in parenting skill, global impression of improvement, parent satisfaction, and cost of treatment.
Endpoint(s)	The primary outcome in the trial is the average daily crying time over 14 days measured by a daily diary completed by infant's parents. Secondary outcomes include average crying time over the first seven days, total crying time over 14 days, parent confidence in parenting skill at day 14, global impression of improvement at day 14, parent satisfaction and experience at day 14, adverse events data and basic direct cost of treatment.
Study Design	Single-blinded two-arm parallel pragmatic randomised multicenter international UK led clinical trial

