Study procedures	
Recruitment: Thirty UK, Australian and Swiss osteopaths will recruit participants in their own clinics. In Switzerland, at least 10 osteopaths are to be recruited. When a parent with a crying, distressed and unsettled baby calls the clinic to book an appointment, the osteopath, or their receptionist, will determine whether the baby fits the inclusion criteria, inform the parent about the study, and send them an invitation letter, the participant information leaflet and a consent form. All those interested in the study will be asked to record the number of minutes their baby cries in the 24 hours preceding their booked appointment. When the interested parents turn up for their baby's consultation they will be given the chance to ask questions about the study and asked if they want to participate. After providing their informed consent, parents will have their baby examined and screened to check overall health. If the baby is healthy, they will formally be enrolled in the trial and receive a unique identification study number (ID) and the parent will be asked to complete the baseline questionnaire online on a dedicated GCP and Data protection act compatible eCRF based in the Netherlands (CastorEDC) using the baby's unique ID.
 
Randomisation, allocation and blinding: Block randomization is used to generate the randomization list to allocate patients to either the study or control interventions. Infants will be allocated to their group after baseline values are collected using the online data entry and patient management system (CastorEDC). There will be a standardised communication protocol between the osteopath and the parent during both the study and control intervention. The parents will therefore be 'blinded'. The parents will NOT be informed which treatment arm their infant has been assigned to, but they will be aware that the infant is receiving either the targeted or generic tension release. The parent will be present throughout the treatment and free to observe the delivery of the intervention. For the analysis the statistician will be blinded to the coding of each group.
 
Data collection: Prior to the first treatment parents will complete a baseline questionnaire, a parenting confidence questionnaire, and a 24 hour crying diary. Parents will be required to complete an online crying diary every day for 14 days and record the dates and time of all treatments given. All participating parents will receive a questionnaire for follow-up information at 14 days, containing the parenting confidence questionnaire, a global impression of improvement question and a parent satisfaction questionnaire (please see section on data collection and outcomes). 14 days after randomisation (the first consultation), after completion of all questionnaires, parent can be informed in which treatment arm their infant was allocated to.

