There will be a standardised communication protocol between the osteopath and the parent/carer during both the OMT and control intervention sessions. It will be delivered at pre-set intervals during each session and include comments such as “your baby is doing very well”, “I have nearly finished checking and treating your baby”, “a few more minutes” and “we have now finished the treatment”. Each intervention session will last between 10 and 20 minutes. The osteopaths will be permitted to make soothing and/or playing noises with the infant during these sessions.

Should the parent wish to ask questions about the hands-on touch, the osteopath can talk in general terms about the explanatory theories associated with gentle light touch care but not about the touch they are giving, as the parent has consented to be blinded to this.

A parent/carer will be present throughout the treatment session and free to observe the delivery of intervention. However, parents/carers will remain 'blinded' throughout the active phase of the trial so that outcomes are not biased a priori by parent/carer expectations. Naming both intervention arms with equal suggestibility with respect to treatment supports this intention. To assess blinding, at the two-week follow-up, each parent/carer will be asked which group they believe their infant was allocated to, we will then compare these guesses between both groups using a Fischer's exact test.

Once the participant has completed and returned their follow-up questionnaire and their crying diary they can be informed about their infant's allocation. If they do not complete their follow-up information, their allocation can be divulged at 21 days or after, post randomisation. Unblinding of the parent will occur in the case of serious adverse events and or complaint and withdrawal from the trial.

To maintain blinding during statistical analyses, the statistician will also be blinded to group identity.

Data collection and management

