In Switzerland, patients are to be recruited by co-investigators during a six month period. Prior to the first treatment, a parent/carer will complete a baseline questionnaire, a parenting confidence questionnaire, and a 24-hour crying diary. These questionnaires will be made available using CastorEDC, a Dutch based secure data management system for collecting research related data. Osteopaths will be encouraged to build rapport with each parent/carer and offer as much counsel and support as necessary. The interval between treatments will be determined by the treating osteopath in consultation with the parent(s)/carer(s) of the infant. Parents/carers will be required to complete an online crying diary every day for 14 days as well as recording the dates and times of all intervention sessions attended.

All participating parents/carers will receive an electronic follow-up questionnaire at 14 days post initial intervention. It contains a second parenting confidence questionnaire, a global impression of improvement questionnaire and a parent satisfaction questionnaire.

Parents will receive a reminder to complete their follow-up questionnaire and diary on day 18 post randomisation if no returns are received.

Table 1 Data collection time points

Baseline	Over 14 days	14 days post randomisation

 • Last 24 hours crying time • Age of mother • Age of infant (weeks and days) • Gestational age (weeks and days) • Gender of infant • Birth weight • Current weight • Number of other siblings • Parent/carer, confidence in parenting * • Parent/carer status (alone or co-parenting) • Number of other children 	
 • Number of minutes of crying time per 24 hours over 14 days • Adverse events: All serious adverse events will be reported to the study team immediately by either the treating clinician osteopath or by the parents/carers directly to the study team either by telephone or by email, depending on the nature of the event. 	
 • Parent confidence in parenting * • Parent satisfaction and experience with osteopathic treatment • Parent rated: Global change score • Other co-treatments used (tick list question) • Information about unexpected and or unwanted outcomes • Group allocation belief

*(Crncec *et al* 2008, Karitane Parents' Confidence Questionnaire)

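### Parents can be told the arm before their follow-up data are in, and nothing closes or flags what they report afterwards

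*Protocol*

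**What the plan says.** The Blinding text in section 4.3 gives the purpose: "parents/carers will remain 'blinded' throughout the active phase of the trial so that outcomes are not biased a priori by parent/carer expectations". It then sets three disclosure rules.

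- Parents who return their data: "Once the participant has completed and returned their follow-up questionnaire and their crying diary they can be informed about their infant's allocation".
- Parents who do not: "If they do not complete their follow-up information, their allocation can be divulged at 21 days or after, post randomisation".
- Events: "Unblinding of the parent will occur in the case of serious adverse events and or complaint and withdrawal from the trial".

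The synopsis (Study procedures) words the routine rule differently. At 14 days after randomisation, "after completion of all questionnaires, parent can be informed in which treatment arm their infant was allocated to". It does not mention the diary in that sentence.

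On late returns, section 4.3 (Data collection and management) says: "Parents will receive a reminder to complete their follow-up questionnaire and diary on day 18 post randomisation if no returns are received".

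The outcomes come from the same parents. According to the synopsis, "The primary outcome in the trial is the average daily crying time over 14 days measured by a daily diary completed by infant's parents", and section 4.3 adds: "Parents/carers will be required to complete an online crying diary every day for 14 days". Table 1 places parenting confidence, satisfaction and experience, global change and the parent's belief about allocation at 14 days. Section 5.2 counts a diary as usable if it has at least eight entries, averages the available days and analyses complete cases.

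**The concern.** In this trial the parent is the outcome assessor. The treating osteopaths cannot be blinded, and section 2 says a no-touch control was ruled out because parents could not have been blinded to it. Parental blinding is therefore the main protection against reporting bias.

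The day-21 rule applies only to parents whose outcome data are still outstanding, and it takes effect three days after they are reminded to send those data. A parent who is told the arm and then answers is reporting with knowledge of it. Global change is a retrospective judgement of improvement and is easily coloured by that knowledge. The group-belief item is affected in another way: a parent who has been told is no longer guessing. Such answers would push the Fisher test towards failed blinding even if blinding had held throughout the 14 days.

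**Working it through.** **1. Timeline from the protocol**

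| Day after randomisation | Event | Source |
|---|---|---|
| 1–14 | Daily diary | Section 4.3 |
| 14 | Follow-up questionnaire; disclosure possible after all questionnaires | Section 4.3; synopsis |
| 18 | Reminder for outstanding questionnaire and diary | Section 4.3 |
| 21 onward | Disclosure possible although data are outstanding | Section 4.3 |

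The reminder shows that returns after day 14 are expected. The gap between reminder and permitted disclosure is 21 − 18 = 3 days. No last date for returns is given.

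**2. The two routine conditions**

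Section 4.3 needs questionnaire and diary. The synopsis needs all questionnaires. The synopsis elsewhere lists the diary separately from the questionnaires, which suggests the diary is not included. Section 4.3, however, uses the word questionnaires for a baseline list that includes the 24-hour crying diary, which suggests it may be. The text does not settle the matter.

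**3. What happens to data supplied after disclosure**

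Section 5.2 sets a minimum number of entries but no condition on when they were recorded or on blinding status. Because the analysis is complete-case, a late diary with eight entries counts as observed. No section records the disclosure date, closes the parent's follow-up at that point or excludes later entries.

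**4. Which outcomes are exposed**

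- Day-14 questionnaire (global change, satisfaction and experience, parenting confidence) and group belief: any answer given after disclosure.
- Primary diary, day-21 route: only days filled in from recall more than a week late.
- Primary diary, event route: a serious adverse event or complaint could unblind a parent within days 1–14 while the diary continues. For withdrawal, section 8.3 uses the data collected up to that point.

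**5. Scale for the primary outcome**

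The protocol gives no figure for late returns, so there is none to reproduce. Its SD (46 min), target difference (30 min) and 48 infants per arm are used only for scale. As a check, 2 × [46 × (1.960 + 1.282)/30]² = 49.4, so 50 per arm against the stated 48; this gap does not affect the present point.

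Two assumptions that are not in the documents:

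- f = share of analysed parents in each arm who record the diary after disclosure, 5–10%
- d = net between-arm reporting shift among them, 10–30 min/day

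Bias in the group difference = f × d:

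- low: 0.05 × 10 = 0.5 min (0.5/30 = 2% of target)
- high: 0.10 × 30 = 3.0 min (3/30 = 10% of target)

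Standard error of the difference = 46 × √(2/48) = 9.39 min. Two-sided type I error = Φ(−1.96 + bias/SE) + Φ(−1.96 − bias/SE):

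- f = 5%, d = 30: bias 1.5 min, type I error 5.3%
- f = 10%, d = 30: bias 3.0 min, type I error 6.2%

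**The case against.** The strongest reply is that the route to the primary outcome is narrow. The diary is prospective and daily, and day 21 falls a week after its last day. Blinding is promised for the active phase, and the day-21 rule respects that. A parent would have to neglect the diary, ignore the reminder, be told the arm (the rule permits disclosure but does not require it) and then fill in at least eight days from memory. The pilot reported good compliance with electronic capture. This stands, and it is why the questionnaire outcomes and the belief item come first here.

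A second reply is that entry windows belong in a data-management plan or an SAP that is not shown, and that section 8.2 says data changes are logged. This stands only in part. The disclosure rule is fixed in the protocol and tied to a calendar day instead of to closure of follow-up. Section 8.2 also excludes crying diaries from the data that CastorEDC captures, so its log cannot be relied on to date them.

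Three stronger readings are tempting, but the documents do not support them.

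- *The synopsis permits disclosure on questionnaires without the diary.* That is one reading of loose wording. What is certain is that the two places differ.
- *The 15% drop-out allowance, 0.15 × 120 = 18 infants, measures how many parents would report unblinded.* Drop-outs are those expected to supply no outcome. The complete-case analysis omits them, so they cause no reporting bias of this kind.
- *The bias could reach 6 minutes, a fifth of the target.* That needs 10% late returns and a 30-minute shift in opposite directions in the two arms. The net shift is then 60 minutes, twice the target difference and half the assumed 120-minute mean. Nothing in the protocol supports it.

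**Conclusion.** The point holds as a minor but real gap. The protocol allows routine disclosure before follow-up data are in, states the condition differently in two places, and says nothing about data supplied afterwards. Late answers from parents who know the arm can therefore be analysed as if blinded.

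The main exposure is the day-14 questionnaire outcomes and the blinding test. By the day-21 route the primary diary is exposed only where it is completed late from recall.

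The size cannot be derived from the documents. Under the assumed 5–10% late returns and 10–30 minute net shift, the bias in crying time is 0.5–3 minutes per day, 2–10% of the 30-minute target. If few returns are late it is close to nothing. The case for changing the text is that the repair is cheap, not that the primary result is in danger.

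**What to change.** 1. Use one condition in the synopsis and section 4.3: routine disclosure only after both questionnaire and diary have been received, or after that parent's follow-up has been declared closed.
2. Record the disclosure date for every parent, whatever the route.
3. In the primary analysis, treat as missing any diary day or questionnaire answer that the parent recorded after disclosure. Apply this also after unblinding for a serious adverse event, complaint or withdrawal; the grounds for that unblinding need no change.
4. Exclude from the blinding test any parent who was told the arm before answering the belief item.
5. Keep diary days recorded before disclosure even if they are transcribed later. The relevant date is when the parent recorded the entry. An entry lock in CastorEDC alone would not govern paper diaries and could discard data recorded while blind.

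The cost is a few sentences of protocol text and one date field. The drawback is that a few very late returns become missing, in a trial whose section 5.2 already says that missing data cannot be assumed to be missing at random. The planned worst-case sensitivity analysis would cover those cases for the primary outcome.

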3.2 Primary and secondary endpoints

The primary endpoint

Reduction of average crying time over two weeks between the active treatment compared to the control. The crying diary used in this trial has been validated against 24-hour recordings of infant vocalisations in a general population sample over a 7-day period (Barr et al., 1988). Correlation between parent/carer noted crying and recorded negative vocalisation was $r=+0.90$ ($p=0.001$). In the population sample of 409 eligible participants, 91% of the diaries received were completed sufficiently for analysis. The set minimal clinically important difference is of 30 minutes crying reduction per day.

Secondary endpoints

Parenting confidence is assessed using the Karitane Parenting Confidence Scale (Črnčec et al., 2008). This 15-item questionnaire has a four level Likert scales (no, hardly ever, =0, no, not very often=1, yes, some of the time=2, yes, most of the time=3) with higher scores indicating better parenting confidence (range from 0 to 45). The instrument showed good internal consistency (Cronbach's alpha=0.81), test-retest reliability ($r=0.88$) and high transcultural validity in Portuguese (Pereira et al., 2018), Danish (Pontoppidan et al., 2019), Japanese (Usui et al., 2020) and Nepali (Shrestha et al., 2016). Reliability change index identified a change of six points as the minimal clinical important difference.

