5.2 Handling of missing data and drop-outs

Missing data from diaries will be accepted if at least eight separate entries over two weeks are provided. The average daily crying time will then be provided by averaging the crying time over the available days. As missing data cannot be assumed to be missing at random, complete case analysis is to be done. A sensitivity analysis will then evaluate effects on results with the worst-case scenario (imputation of highest observed effect if in control and lowest if in OMT group).

Drop-outs from treatment are to be followed-up and questionnaires delivered as if treatment had continued (ITT approach). Data from participants who have dropped-out or could not be followed will be replaced by new subjects.

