8.2 Data recording and source data

No copy of the aggregated data will be kept in Switzerland. The UCO holds responsibility for managing data and archiving data for the international study. Most data is captured directly electronically using CastorEDC. This dedicated system for capturing clinical trial data will capture and manage all data apart for Consent forms, Participant Logs and Crying Diaries.

The Consent Form will be stored in the treating osteopath's patient note file and an additional copy will be kept by the parent. Participant Logs, including names and contact details, are kept by co-investigators. Number of parents invited to participate and refusals are anonymised and summarised to be reported to the Principle Investigator. Transfer from paper forms diary entries to the CastorEDC will be done by the Chief Investigator for data quality control. Double data entry by a second person is planned to detect and avoid transcription errors.

CastorEDC

The software (CastorEDC <https://castoredc.com>), developed by Ciwit B.V, in the Netherlands, provide facilities for electronic case report forms, survey questionnaire data capture and participant case history tracking information.

Castor complies with all applicable laws and regulations, including ICH E6 Good Clinical Practice (GCP), 21 CFR Part 11, EU Annex 11, General Data Protection Regulation (GDPR), HIPAA (US), ISO 9001 and ISO 27001. By using Castor, researchers are enabled to comply with these laws and regulations. Castor is a validated system and approved by external auditors. Trevalco audited Castor EDC in November 2017 for GCP compliance to ensure compliance (ISO/IEC 27001 – 0025833).

Confidentiality

Anonymity of the participants is ensured through the allocation of a unique study identifier. Confidentiality and blinding are ensured by access controls set by the study data manager. Co-investigators have access to all entries within sites. They however can only access to files related to participants they are following.

Backup and storage

All data throughout the trial period is stored on the secure and backed up CastorEDC servers which complies with current EU and UK legislation and standards. All data access and changes are tracked and logged. All study material and details including the final anonymised data set will be archived and stored in a university repository for 25 years.

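### The only stated diary reminder comes on day 18, after the 14-day diary has ended, and no entry window is set, so entries recalled 4 to 17 or more days later are not excluded from the primary outcome

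*Protocol*

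**What the plan says.** Section 4.3 (Data collection and management) sets the schedule: "Parents/carers will be required to complete an online crying diary every day for 14 days". The Synopsis, under study procedures, also describes a daily online diary. The one reminder to parents in the protocol is in the same part of 4.3: "Parents will receive a reminder to complete their follow-up questionnaire and diary on day 18 post randomisation if no returns are received".

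Section 5.2 fixes what counts as a usable diary: "Missing data from diaries will be accepted if at least eight separate entries over two weeks are provided". It then says: "The average daily crying time will then be provided by averaging the crying time over the available days". Neither sentence mentions when an entry was made.

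On disclosure to parents who have not returned their data, section 4.3 (Blinding) says: "If they do not complete their follow-up information, their allocation can be divulged at 21 days or after, post randomisation".

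On capture, section 8.2 says of the electronic system: "This dedicated system for capturing clinical trial data will capture and manage all data apart for Consent forms, Participant Logs and Crying Diaries". It goes on: "Transfer from paper forms diary entries to the CastorEDC will be done by the Chief Investigator for data quality control". The same section states that data access and changes on the electronic servers are logged.

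Section 3.2 supports the diary by its agreement with 24-hour recordings (r = 0.90), and section 7.2 describes such diaries as accurate to within 5 minutes.

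**The concern.** The diary is the sole source of the primary outcome, and its credibility rests on being kept day by day. The protocol offers no evidence on the accuracy of daily minutes written down days or weeks afterwards. Such figures may reflect a parent's overall impression of whether the baby improved, which the trial measures separately as global change.

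The reminder goes to parents from whom nothing has been received, and it asks them to complete the diary. For an online diary due daily, nothing received means that no day has been entered, so the parent may well reconstruct the fortnight.

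Four other parts of the plan would be affected:

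- The worst-case sensitivity analysis in 5.1 and 5.2 deals with missing outcomes. A back-filled diary is not missing, so that check does not reach it.
- The monitoring rule in 5.1 concerns parents who do not complete their diaries. A back-filled diary could pass as complete.
- The first-week outcome, the white-noise test for each infant and the trend analysis all need true daily values.
- An entry made once the parent knows the allocation is no longer a blinded outcome.

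**Working it through.** **Inputs.** Diary days 1 to 14, reminder on day 18 and possible disclosure from day 21 (all 4.3); minimum of eight entries (5.2); SD 46 minutes, target difference 30 minutes, 48 per arm, 90% power, two-sided 5% (5.1). I assume that diary days and reminder day are counted on the same scale.

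**Recall delay.** Delay = day of entry minus diary day.

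- Entry on day 18: 18 − 1 = 17 days for day 1 (17/7 = 2.4 weeks) and 18 − 14 = 4 days for day 14. The mean is (17 + 4)/2 = 10.5 days.
- First-week days are recalled over 11 to 17 days.
- If only the most recent eight days (7 to 14) are filled in, the delays are 11 down to 4 days, mean 7.5. That diary would meet the minimum in 5.2.
- Entry on day 21: 20 days for day 1 and 7 days for day 14. The protocol gives no closing date, so this is not a limit either.

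**Capture mode, side by side.** Section 4.3 and the Synopsis make the diary online. Section 8.2 lists crying diaries among the items that the electronic system does not capture, and then describes transcribing paper diary entries. Both cannot describe the standard route. The difference matters because electronic changes are logged, whereas no entry date is stated for a paper diary day.

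**Disclosure, side by side.** Section 4.3 allows disclosure once questionnaire and diary are both back, or from day 21 if follow-up is incomplete. The Synopsis ties disclosure after 14 days to completion of the questionnaires and does not name the diary. Neither place closes the diary at disclosure.

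**The plan's sample size, as a base for illustration.** n per arm = 2(1.960 + 1.282)² × 46²/30² = 49.4, so 50, against the stated 48. Power at 48 per arm: 30/(46√(2/48)) = 3.195; 3.195 − 1.960 = 1.235; power 0.89. The stated figure is reproduced closely enough, and nothing below depends on the small gap.

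**Illustration under assumed inputs.** The protocol gives no share of late diaries and no size of recall error.

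| Assumed effect of recall | Power at 48 per arm |
|---|---|
| None | 0.89 |
| 30-minute contrast diluted by 5% | 0.86 |
| diluted by 10% | 0.82 |
| diluted by 20% | 0.72 |
| diluted by 30% | 0.61 |
| SD raised from 46 to 50 | 0.84 |
| SD raised to 55 | 0.76 |
| SD raised to 60 | 0.69 |

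**Bias of the contrast.** Let p be the share of back-filled diaries in an arm and b their mean shift. The bias of the difference is p₁b₁ − p₀b₀. If 10% to 20% of one arm's diaries shift by 20 to 40 minutes, that arm's mean moves by 0.10 × 20 = 2 to 0.20 × 40 = 8 minutes. With equal shares and shifts in both arms the difference is not biased at all.

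**The case against.** The strongest reply is that silence is not a rule. Entry windows, field locks and the handling of late days often sit in the eCRF set-up, data-management documents or a statistical analysis plan, none of which is shown. This stands in part. A reader might infer that the plan counts late entries in full, but no section says so; the text only fails to exclude them. The reminder schedule, the acceptance rule and the capture mode, however, are all fixed in this protocol, and a later analysis plan cannot recover entry dates that were never recorded.

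Second, the reminder may only chase the return of a diary that was kept daily. Section 4.2 gives parents the diary in advance, and the Blinding text in 4.3 speaks of completing and returning it. This reading is fair, particularly for paper. The reminder's wording does not separate it from filling the diary in.

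Third, a reader might infer that contemporaneous and recalled days cannot be told apart. For electronic entries this fails: changes are logged (8.2), and the data manager reports weekly on data quality (8.1). It can hold only for paper. The change history records a move from paper to the electronic system, so the exception in 8.2 may be a leftover. It still needs reconciling.

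Fourth, parents are blinded, and section 4.3 reports that blinding worked in the pilot, so a shift confined to one arm is an extreme case. This stands.

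**Conclusion.** The point holds as a weakness in how the primary outcome is collected. The only stated reminder falls four days after the last diary day and asks for completion of the diary. No timing condition applies to the eight entries. Entries recalled 4 to 17 or more days later are therefore not excluded, and from day 21 they could follow disclosure of allocation. Sections 4.3 and 8.2 also contradict each other on capture.

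The size is unknown. A reader might turn the assumed 2 to 8 minute movement into a bias of 7% to 27% of the 30-minute target (2/30 to 8/30). That needs the whole assumed shift to fall in one arm, and the documents do not support it. The contrast is biased only so far as recall differs by arm. The dilution case above is one way this could happen, if recall pulls both arms towards a common impression when a true effect exists. Nor is two and a half weeks a limit: 17 days applies to day 1 of a diary filled in on day 18, and no closing date is stated. The point warrants a change because the remedy costs little, not because harm has been shown.

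**What to change.** 1. In 4.3, send an automatic prompt from the electronic system during days 1 to 14 whenever a day's entry is missing.
2. Reconcile 8.2 with 4.3 and the Synopsis so that the online diary is standard. Any paper diary should record the date on which each day was filled in.
3. Word the day-18 reminder as a request to return a diary already kept, not to fill one in from memory.
4. Accept no diary entry after allocation has been disclosed to the parent, and align the Synopsis and 4.3 on when disclosure is allowed.
5. Add a sensitivity analysis of the primary outcome that leaves out late-entered days, with the window for late entry fixed before unblinding.

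The cost is a minor eCRF set-up, protocol wording and one extra analysis. I would not make a short lock, such as 48 hours, the primary rule. Turning late days into missing ones would push some infants below eight entries, out of the complete-case analysis and into worst-case imputation. That trade-off is debatable, and the sensitivity analysis avoids it.
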